In order to detect statistical differences between the two study arms, as well as correlation between personality traits, quality of life, frailty, hepatic encephalopathy and patient characteristics (age, primary diagnosis, MELD, etc), we expect that a sample size of 500 should be suitable for this pilot study.

PROVISIONS TO MONITOR THE DATA TO ENSURE THE SAFETY OF PARTICIPANTS

Safety of the intervention, specifically risk of falls and muscle strains, will be assessed on a weekly basis with telephone calls to each participant. Physical therapist will tailor exercise regimens to each patient's physical function in order to minimize risk of falls. The safety of the intervention will be assessed at bi-monthly research team meetings.

PROVISIONS TO PROTECT THE PRIVACY INTERESTS OF PARTICIPANTS

Only research team members will contact participants once they enroll in the study. The frequency of communication will be clearly outlined to each participant prior to enrollment to ensure appropriate expectations.

Only IRB approved personnel will have access to the data. All data will be stored on FSM shared drive-accessed only by approved personnel. All data is accessed through password protected computer kept in locked offices. All patient identifiers will be stored in a separate password protected file.

All publications will include only aggregated data and no patient identifiers will ever be reported. Data will be stored until 3 years after the end of the project and will be destroyed.

COMPENSATION FOR RESEARCH-RELATED INJURY

None

ECONOMIC BURDEN TO PARTICIPANTS

None

CONSENT PROCESS

PT Intervention participants

Informed consent will be obtained from patients or their POA prior to any data collection. Consent will be obtained by research coordinators or other members of the research team using an online consent form or in Hepatology and Transplantation Evaluation Clinic, where patients will be enrolled. Dedicated time will be reserved for after the visit to explain the research study and highlight risks/benefits. Participants will be asked to summarize their own understanding of the study, as well as potential risks/benefits, in order to ensure capacity to enroll. Consent will be obtained in English if the patient is English-speaking.

A waiver of consent will be requested for the retrospective EDW data extraction for the historical control group. It meets criteria for a waiver of consent as listed on the IRB website: 1) The research is not FDA regulated. 2) The research does not involve non-viable neonates. 3) The research involves no more than minimal risk to subjects. 4) The waiver or alteration will not adversely affect the rights and welfare of the subjects. 5) The research could not be practicably carried out without the waiver. Patients will not be required to complete any tasks as part of the control study and will not be subject to any risks. Seeing as there are approximately 300 patients who have received a liver transplant at Northwestern since 1/2018, it would be impractical to consent each patient. Moreover, many patients have passed away or likely no longer follow up closely at Northwestern. Obtaining consent from these deceased patients would be impossible and obtaining consent from patients who no longer follow at NMH would be very difficult. Although consent could be obtained from deceased patients' families, this could adversely affect the rights of privacy for these families and cause more emotional harm. 6) The research could not be carried out without using private information in an identifiable format. 7) Whenever

appropriate, the subjects will be provided with additional pertinent information after participation.

QOL Assessment participants

Informed consent will be obtained from patients or their POA prior to any data collection. Consent will be obtained by research coordinators or other members of the research team using a verbal consent process over the phone, where patients will be enrolled. Dedicated time will be reserved to explain the research study and highlight risks/benefits. Participants will be asked to summarize their own understanding of the study, as well as potential risks/benefits, in order to ensure capacity to enroll. Consent will be obtained in English if the patient is English-speaking.

NON-ENGLISH SPEAKING PARTICIPANTS

Non-English speakers will not be included in this study.

WAIVER OR ALTERATION OF CONSENT PROCESS

- *Adults Unable to Consent or Cognitively Impaired Adults:*
 - Consent will be required for all participants.
 - Ability to provide consent will be assessed by the research team member introducing the research study and obtaining consent. Patients' capacity to consent will be assessed by asking the patients to clearly state the purpose of the study and what the study entails. They will be asked to outline the potential benefits and consequences of the study. They will be assessed on their understanding that the study is voluntary and their understanding that deciding not to participate will not impact their medical care negatively in any way.
 - If a participant is unable to provide consent, consent will be obtained from the participant's durable power of attorney for health care, court appointed guardian for health care decisions, spouse, and adult child, in this order.
 - If a patient is determined to not have capacity to provide consent, the research study will still be explained to the patient in a level suitable to their understanding.
- *Process to Document Consent in Writing*

PT Intervention participants

Please see Written Consent Form attached. This is the separate consent form for the LIFT+/- REAP study.

QOL Assessment participants

Please see the Verbal Consent form. This is the separate consent form for the QOL assessment study.

The researchers request a waiver of written consent for the QOL assessment study participants. The verbal consent form contains all elements of consent disclosure, and the QOL assessments are minimal risk. Interventions are limited to surveys and an EDW query of their medical records. These interventions would not require consent in a standard clinical context.

Moreover, the researchers have found that eConsent has not been practicable for the study population, which is generally elderly, chronically ill, and not technically savvy. As such, the researchers estimate that 30% of study candidates have been lost due to technical difficulties with the eConsent process.

PROTECTED HEALTH INFORMATION (PHI AND HIPAA)

- This study does involve the creation and use of PHI.
- HIPAA authorization will be obtained from all patients seen in Hepatology and Transplantation Evaluation Clinic, the setting in which participants are recruited.
- Specific PHI to be obtained from the EDW and chart review are outlined in Appendix A, B.
- QOL Assessment participants
The researchers request a waiver of written HIPAA authorization for the QOL assessment study participants. The researchers have found that electronic HIPAA authorization has not been practicable for the study which is generally elderly, chronically ill, and not technically savvy. As such, the researchers estimate that 30% of study candidates have been lost due to technical difficulties with the electronic HIPAA authorization process.

This study could not be practicably conducted without access to the participants' PHI. The variables (described on page 10) are required to assess correlation between survey responses and clinical outcomes. The clinical variables are also required to control for confounders when analyzing survey data. Therefore, access to PHI is critical to the goals of this study.

Finally, the use of the PHI is of no more than minimal risk to the participants. The NM EDW will be used to query the participants' medical records and data will be kept on an FSM managed server. For more information, please refer to the "DATA MANAGEMENT AND CONFIDENTIALITY" section of this protocol. The PHI collected for these participants will not be reused or disclosed to any other person or entity, and the identifiers will be destroyed at the time of IRB closure.

-

QUALIFICATIONS TO CONDUCT RESEARCH AND RESOURCES AVAILABLE

- Given the number of patients seen in Hepatology (10 patients)/Transplantation Evaluation Clinic (8 patients) on a weekly basis, it will be feasible to recruit the required number of patients necessary for the study.
- The study will be conducted and completed by a research team under the leadership of the Principle Investigator, [name]. Study analysis will be performed by [name] (dedicated T32 research fellow) and [name] (dedicated research medical student).
- Outside of surveys and testing completed in clinic, no other facilities/resources will be required for this study.
- All members of the research team will review the study protocol to ensure that they are informed of research procedures as well as their individual duties and functions.

MULTI-SITE RESEARCH

This is not a multi-center study.

STU#: 00213159

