Aim 1: To evaluate the feasibility of the LIFT and REAP interventions in patients evaluated for liver transplantation.

Aim 2: To measure the effect of the LIFT and REAP intervention on frailty in patients evaluated for liver transplantation.

Aim 3: To evaluate barriers to the implementation of the LIFT and REAP interventions

Aim 4: To analyze the effects of LIFT and REAP on pre- and post-liver transplant clinical outcomes.

BACKGROUND:

Frailty is defined as a biologic syndrome of decreased physiologic reserve and increased vulnerability to health stressors. The concept of frailty has recently emerged as a critical determinant in the field of cirrhosis and liver transplantation. Frailty impacts pre- and post-transplant clinical outcomes, including waitlist mortality, post-transplant mortality, frequency of hospitalizations and duration of hospital admissions. Although the impact of frailty in liver transplantation has been established in the literature, there is a lack of data supporting effective interventions to decrease frailty prior to liver transplantation. Moreover, the studies that have tested interventions to improve physical function have relied on frequent supervised physical therapy sessions and access to exercise equipment that it is not financially or logistically feasible for the majority of patients. Patient engagement in PT also remains a critical barrier to overcome to decrease frailty in preparation for liver transplantation. Developing a practical and effective intervention to consistently engage patients in physical activity and decrease frailty is essential to improving clinical outcomes in the pre- and post-liver transplant setting.

Our goal is to pilot test a novel PT intervention to decrease frailty in pre-transplant patients. We have designed a prototype “Liver FrailTy” intervention (LIFT) that includes: PT evaluation, an individualized home exercise prescription (HEP), daily text message reminders to exercise and weekly telephone check-ins with team members. We will also employ “Realistic Effort Action Planning” (REAP), a form of personality-informed motivational interviewing in a subset of patients to potentially enhance patient engagement and adherence to the home-exercise prescription.

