Our central hypothesis is that our LIFT (+/- REAP) intervention will 1) improve adherence to recommended levels of exercise in end-stage liver disease 2) reduce pre-transplant frailty and 3) will improve pre- and post-transplant clinical outcomes.

STUDY ENDPOINTS:

Primary endpoints:

- Frailty (measured by Liver frailty index [LFI])
- Clinical outcomes: placement on LT waitlist, waitlist-mortality, post-transplant mortality, post-transplant disposition (acute rehabilitation, subacute rehabilitation center, home, etc), number of hospitalizations, duration of hospitalizations, liver related complications (ascites, hepatic encephalopathy, variceal bleeding, hepatorenal syndrome, hepatopulmonary syndrome, infections).
- Feasibility (measured by 8-question emailed survey)

[figure not shown]
Secondary endpoints:

- Endurance (measured by the 4-meter walk test).
- Patient adherence to the home exercise prescription (measured by daily diary counts of adherence to prescribed exercises, tracked on the TrueCoach application)
- Degree of hepatic encephalopathy (measured by List Sort Working Memory [LSWM] test and the Flanker Inhibitory Control and Attention [FICA])
- Patient-reported quality of life (measured by various PROMIS questionnaires)
- Feasibility/acceptability (measured by a study-specific questionnaire evaluating the acceptability and feasibility as reported by patients, providers and support staff)

STUDY INTERVENTION(S) / INVESTIGATIONAL AGENT(S):

Home exercise prescription (HEP) detailed below in study design.

PROCEDURES INVOLVED:

Recruitment for Quality of Life Assessment Study:

- A Northwestern Medicine Enterprise Data Warehouse (NMEDW) search will be used to identify all patients who have been seen in Transplant Evaluation Clinic and are currently being considered for liver transplantation or are already on the waitlist or have received a transplant.
- Alternatively, a list of the patients described above will be obtained from the transplant coordinator.

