 - If patients have questions regarding exercise regimen, they will be contacted by a physical therapist.
 - Progress reviewed and exercise regimen potentially adjusted by a physical therapist based on data collected and patient experience.
- *Clinical data collection via NEDW and review of EMR (every 4 weeks)*
 - Number of hospitalizations, intensive care unit admissions, duration of hospitalizations, development of decompensating events (ascites, hepatic

encephalopathy, variceal bleeding), transplant status, type of LT (living donor LT, simultaneous liver-kidney), duration of hospital admission for LT, duration of ICU admission for LT, duration of intubation post-LT, post-transplant discharge disposition, date of death, cause of death, post-transplant complications (rejection, infection, biliary complications).

- *Clinic visits (every 3 months, same tools as noted above)*
 - Patient-reported quality of life assessment
 - Hepatic encephalopathy assessment
 - Frailty assessment, 4-meter walk test (standard of care)
 - Physical therapy in person update (standard of care)
 - Data collection via NMEDW extraction and chart review: Number of hospitalizations, intensive care unit admissions, duration of hospitalizations, development of decompensating events (ascites, hepatic encephalopathy, variceal bleeding), transplant status, type of LT (living donor LT, simultaneous liver-kidney), duration of hospital admission for LT, duration of ICU admission for LT, duration of intubation post-LT, post-transplant discharge disposition, date of death, cause of death, post-transplant complications (rejection, infection, biliary complications).
- Feasibility assessment (for those who remain in the study for at least 1 month or until receiving a liver transplant; surveys emailed)
 - Tool: 8 -question survey emailed to eligible subjects as noted above.
 - Data collected via REDCap.
 - Time: < 3 minutes
 - Appendix G

All participants who enroll for the PT intervention will be randomized (1:1) into the LIFT subgroup or the LIFT + REAP subgroup at 2 weeks after enrollment/baseline session. The LIFT subgroup will continue to follow up as detailed above. The LIFT + REAP subgroup will undergo Realistic Effort Action Planning (REAP), which is described below:

LIFT + REAP subgroup:

Follow up:

- *REAP introduction (2 weeks after enrollment, via telephone/videoconference, time: 30 minutes)*
 - Performed by a member of the research team.

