 - Number of hospitalizations, intensive care unit admissions, duration of hospitalizations, duration of intensive care unit admission, development of decompensating events (ascites, hepatic encephalopathy, presence of esophageal/gastric varices, history of variceal bleeding, hepatorenal syndrome, hepatopulmonary syndrome, infections), transplant status, date of death, cause of death, placement on LT waitlist, delisting from LT waitlist, date of transplant, type of LT (living donor LT, simultaneous liver-kidney), duration of hospital admission for LT, duration of ICU admission for LT, duration of intubation post-LT, post-transplant discharge disposition, post-transplant complications (rejection, infection, biliary complications, hypertension, hyperlipidemia), liver frailty index scores, Karnofsky Performance Status Scores, body mass index (BMI), and laboratory data (platelets, serum sodium, serum creatinine, PT/INR, total bilirubin, albumin, calculated MELD).

DATA AND SPECIMEN BANKING

Data/specimens will not be banked for future use.

The data collected in this study will also be used in the Functional Assessment in Liver Transplantation study (STU00203582), The Role of Circadian Dysfunction in Hepatic Encephalopathy in Patients with Cirrhosis study (STU00204423), and the Personality, QOL and Frailty in Liver Transplantation study (STU00212668).

SHARING RESULTS WITH PARTICIPANTS

Study results will not be shared with participants or anyone else.

STUDY TIMELINES

Patients will be prospectively enrolled in the study from 9/13/2020 vs date of IRB approval to 7/31/2025. Patients in the Quality of Life Assessment arm will remain enrolled in the study while on the liver transplant waitlist and until 3 years after liver transplantation or up to a maximum of 5 years if not listed for liver transplantation. Patients in the PT Intervention arm will remain enrolled in the study while on the liver transplant waitlist and until 1 year after liver transplantation or up to a maximum of 5 years if not listed for liver transplantation. The estimated date for completion of primary analyses is 9/1/2025.

INCLUSION AND EXCLUSION CRITERIA

PT Intervention Study

Inclusion (criteria will be confirmed during consent process and during in-clinic physical therapy evaluation)

- Patients with a diagnosis of liver cirrhosis being evaluated for liver transplantation in hepatology/transplant evaluation clinic
- English-speaking

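### Deaths before or without listing belong to no named endpoint, although patients are randomised during transplant evaluation, and post-transplant mortality compares the arms only in patients selected after randomisation

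*Combined protocol and SAP*

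**What the plan says.** **Who enters and when.** The inclusion criteria for the PT Intervention Study admit "Patients with a diagnosis of liver cirrhosis being evaluated for liver transplantation in hepatology/transplant evaluation clinic". Listing is not required. Under PROCEDURES INVOLVED, participants "will be randomized (1:1) into the LIFT subgroup or the LIFT + REAP subgroup at 2 weeks after enrollment/baseline session". Randomisation is tied to the calendar, not to listing or transplant.

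**What is measured.** STUDY ENDPOINTS gives the primary clinical outcomes as "Clinical outcomes: placement on LT waitlist, waitlist-mortality, post-transplant mortality, post-transplant disposition", then hospitalisations and liver complications. These are the only mortality endpoints. No secondary endpoint concerns death, and waitlist mortality is not defined.

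**What is recorded.** In both arms the four-weekly record review covers "post-transplant discharge disposition, date of death, cause of death, post-transplant complications", with no restriction to listed patients. STUDY TIMELINES keeps PT patients in the study while waitlisted and "until 1 year after liver transplantation or up to a maximum of 5 years if not listed for liver transplantation".

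**What is analysed.** The Statistical analysis section compares LIFT with LIFT + REAP by chi-squared tests and t-tests. It gives no analysis set or denominator. It also plans a survival analysis but names no event, time origin, population or censoring rule. Aim 4 is "To analyze the effects of LIFT and REAP on pre- and post-liver transplant clinical outcomes".

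**The concern.** The randomised population is everyone under evaluation, but the mortality endpoints are attached to later states that only some patients reach. Two problems follow.

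First, a patient who dies during evaluation, or after being declined, fits neither mortality endpoint. The protocol expects such patients, since it provides follow-up of "up to a maximum of 5 years if not listed for liver transplantation". Their deaths are pre-transplant outcomes in a randomised patient, so they bear on Aim 4.

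Second, reaching the list or the transplant happens after randomisation for anyone still in evaluation. "placement on LT waitlist" is itself a primary outcome, and the central hypothesis in BACKGROUND is that the intervention improves outcomes before and after transplant. If adding REAP changes who is listed or transplanted, the patients in those states differ between arms in prognosis. Comparing deaths within them is then no longer a randomised comparison. An arm that gets frailer patients listed could show higher waitlist mortality although nobody extra has died.

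**Working it through.** **Plan's own figure.** There is none to reproduce. The documents give no listing rate, transplant rate or death rate. The only design number, a sample size of 500, is stated without significance level, power or effect size.

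**Where each death falls**

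| Death in a randomised PT patient | Recorded? | Named mortality endpoint |
|---|---|---|
| During evaluation, before any listing decision | Yes | None |
| After being declined, never listed | Yes | None |
| While listed | Yes | Waitlist mortality |
| After delisting | Yes, while in follow-up | Not stated |
| After transplant | Yes, to 1 year after transplant | Post-transplant mortality |

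**Size of a possible spurious difference (all rates assumed).** Suppose REAP changes no patient's risk of death but raises the proportion listed from L to M. Let a be the death risk in patients listed under either arm, b the risk in those listed only because of REAP, and n the risk in those never listed. Then:

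- All-cause mortality in either arm = L·a + (M − L)·b + (1 − M)·n
- Mortality among listed patients: LIFT = a; LIFT + REAP = [L·a + (M − L)·b] / M
- Spurious excess among listed patients = (M − L)/M × (b − a)
- Share of deaths outside the endpoint: LIFT = (all-cause − L·a)/all-cause; LIFT + REAP = (1 − M)·n/all-cause

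Example with L = 50%, M = 60%, a = 10%, b = 30%, n = 40%:

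- All-cause = 0.05 + 0.03 + 0.16 = 24.0% in both arms.
- Among listed patients: 10.0% with LIFT and (0.05 + 0.03)/0.60 = 13.3% with LIFT + REAP, an excess of 3.3 points.
- Outside the endpoint: (0.24 − 0.05)/0.24 = 79% with LIFT and 0.16/0.24 = 67% with LIFT + REAP.

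All 12 scenarios, showing the excess among listed patients in percentage points and, in brackets, the share of deaths outside the endpoint (LIFT / LIFT + REAP):

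| Listed, L to M | a, b, n = 10, 30, 40% | 10, 20, 30% | 15, 25, 25% |
|---|---|---|---|
| 40 to 50% | 4.0 (85% / 74%) | 2.0 (81% / 71%) | 2.0 (71% / 60%) |
| 50 to 60% | 3.3 (79% / 67%) | 1.7 (74% / 63%) | 1.7 (62.5% / 50%) |
| 50 to 55% | 1.8 (80% / 73%) | 0.9 (74% / 69%) | 0.9 (62.5% / 56%) |
| 60 to 70% | 2.9 (71% / 57%) | 1.4 (65% / 53%) | 1.4 (53% / 39%) |

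The excess runs from 0.9 to 4.0 points and the share outside from 39% to 85%. The excess is zero if REAP does not change listing (M = L), or if the additional listed patients carry the same risk as the rest (b = a).

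**Does a change of denominator cure it?** No. Dividing waitlist deaths by all randomised patients gives 5.0% against 8.0% in the example, with all-cause mortality equal. With 250 per arm and a two-sided 5% test (assumed), the calculated chance of rejection over the 12 scenarios is 7% to 31%. The figure of 250 is an upper bound, because 500 covers all groups including the Quality of Life study. Only all-cause death is unaffected.

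**The case against.** A reader might infer that deaths without listing count nowhere. The documents do not support that. Date and cause of death are collected in both arms, never-listed patients stay under follow-up, and the survival analysis has no stated population and could include these deaths. They are recorded but assigned to no named endpoint.

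A reader might also infer that waitlist mortality will be tested among listed patients only, or that death after delisting is excluded. Neither is stated: the denominator and the definition are both missing. The selection point is firm only for post-transplant mortality and disposition, which cannot exist without a transplant. Nor does Aim 4 itself name patients under evaluation as its population; that wording is in Aims 1 and 2.

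On size, the spurious difference requires REAP to change listing. Both arms receive the same exercise prescription, reminders and weekly check-ins, and nothing in the documents supports a particular difference in listing. That objection stands, so the table above is an illustration and not an estimate.

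It can also be said that all-cause death is no simple replacement, because follow-up length depends on listing and transplant and late entrants contribute little. Enrolment runs to 7/31/2025 and the primary analyses are due by 9/1/2025. A patient enrolled on the last day would be randomised about 8/14/2025 and have about 18 days. This also stands, and the fix therefore needs a horizon and a censoring rule.

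None of this supplies an endpoint for the unlisted deaths or a population for the mortality comparison. Silence leaves both to be settled after the data are seen.

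**Conclusion.** The point holds in this form. The trial randomises patients during evaluation but names no mortality endpoint that covers all of them. Comparing arms on post-transplant mortality and disposition conditions on an event after randomisation; for waitlist mortality the same is true if it is analysed among listed patients.

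The structural part rests on the documents alone. The size (0.9 to 4.0 points among listed patients, 39% to 85% of deaths outside the endpoint) rests wholly on assumed listing and death rates and on REAP changing listing. It shows that a misleading difference is possible, not that one is expected.

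It would go too far to conclude that all the clinical outcomes are compromised. LFI, placement on the list, hospitalisations and liver complications are not restricted to listed patients. Since the study describes itself as a pilot, this is a should-fix.

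**What to change.** **STUDY ENDPOINTS.** Add all-cause death from randomisation, in all randomised PT patients whether listed, declined, delisted or transplanted, as the mortality endpoint for LIFT against LIFT + REAP.

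**Statistical analysis.** Make this the event of the survival analysis and state:

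- randomisation as time origin;
- follow-up continued through transplant, so that transplant is not a censoring event;
- a fixed horizon, for example 12 months from randomisation. Follow-up to 1 year after transplant reaches this for anyone transplanted after randomisation. STUDY TIMELINES does not say how long delisted patients are followed, so state that they are followed to the same horizon;
- administrative censoring for late entrants.

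**Existing outcomes.** Keep waitlist mortality, post-transplant mortality and disposition as descriptive outcomes in listed or transplanted patients, without a causal claim between arms. Define waitlist mortality and say how death after delisting is counted. If death before transplant is also reported, treat transplant as a competing event, because otherwise a difference in transplant rates would distort it.

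**Cost.** One added endpoint and a stated horizon and censoring rule. Date of death is already collected. If waitlist mortality is reported, listing and delisting dates must also be recorded in the randomised arms. The protocol names both items for the retrospective controls and the Quality of Life study, but for the randomised arms it names only transplant status.

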- Only the principal investigator and co-investigators listed on this study will have access to harvested patient data.
- Any documents containing identifiable information will be destroyed within five years of project completion using electronic "shredding" software.

POTENTIAL BENEFITS TO PARTICIPANTS

PT Intervention Study:

Improvement in physical function (decreased frailty), which should improve pre- and post-transplantation outcomes, is the primary benefit of participating in the study. Based on the current literature demonstrating the negative impact of frailty on clinical outcomes in liver transplantation, improvement in clinical outcomes with improvement in physical function is likely.

QOL Assessment Study:

There is no direct benefit to participation.

DATA MANAGEMENT AND CONFIDENTIALITY

Only IRB approved personnel will have access to the data. All data will be stored on FSM shared drive-accessed only by approved personnel. All data is accessed through password protected computer kept in locked offices. All patient identifiers will be stored in a separate password protected file.

These data will be presented at national meetings (i.e. American Transplant Congress, etc) and a manuscript will be written for consideration of publication in respected, peer-reviewed journals (i.e. American Journal of Transplantation). All publications will include only aggregated data and no patient identifiers will ever be reported. Data will be stored until 3 years after the end of the project and will be destroyed.

QOL Assessment study

As PHI will be collected under a waiver of written HIPAA authorization, the PHI collected for these participants will not be reused or disclosed to any other person or entity, and the identifiers will be destroyed at the time of IRB closure.

Statistical analysis:

Chi-squared tests will be used to assess differences in categorical clinical endpoints and T-tests will be used to assess differences in continuous clinical endpoints between the LIFT and LIFT + REAP subgroups. Multivariate analysis will be used to assess clinical factors associated with clinical endpoints in each group. Survival analysis will be conducted after controlling for all the variables that are significant during regression analysis.

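### At least nine outcomes are named primary with no stated alpha, hierarchy or success rule; at an assumed 5% per test and independence, the chance of a false-positive primary result is about 30% to 51%

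*Combined protocol and SAP*

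**What the plan says.** The primary list in STUDY ENDPOINTS has three bullets.

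- Frailty: "Frailty (measured by Liver frailty index [LFI".
- Clinical outcomes: "Clinical outcomes: placement on LT waitlist, waitlist-mortality, post-transplant mortality, post-transplant disposition (acute rehabilitation, subacute rehabilitation center, home, etc), number of hospitalizations, duration of hospitalizations", and then "liver related complications (ascites, hepatic encephalopathy, variceal bleeding, hepatorenal syndrome, hepatopulmonary syndrome, infections".
- Feasibility: "Feasibility (measured by 8-question emailed survey".

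None is marked as the main endpoint, and none carries an analysis time point.

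The randomised comparison is set out under PROCEDURES INVOLVED: "All participants who enroll for the PT intervention will be randomized (1:1) into the LIFT subgroup or the LIFT + REAP subgroup", two weeks after the baseline session. For that comparison the Statistical analysis section says: "Chi-squared tests will be used to assess differences in categorical clinical endpoints and T-tests will be used to assess differences in continuous clinical endpoints". Multivariate and survival analyses follow. The sample-size sentence opens "In order to detect statistical differences between the two study arms" and settles on 500, with no effect size, event rate, alpha or power.

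In both arms LFI is measured at home every 4 weeks and in clinic every 3 months. STUDY TIMELINES keeps participants in the PT intervention until 1 year after transplant, or for at most 5 years if never listed. No significance level, sidedness, testing order, multiplicity adjustment or definition of a positive trial appears anywhere.

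**The concern.** When several outcomes are all primary and no rule links them, any one that reaches nominal significance can be reported as a positive primary result. The more outcomes tested, the more likely this is by chance alone. For LFI there is a further choice, because several home and clinic measurements could each serve as the primary one.

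Mixed results are the second problem. If LFI showed no difference but hospital days did, or the reverse, the plan gives no basis for saying whether the trial succeeded. BACKGROUND describes the purpose as "Our goal is to pilot test a novel PT intervention to decrease frailty in pre-transplant patients". That points to frailty as the natural lead endpoint, but the endpoint list does not give it that place.

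**Working it through.** **The plan's own figure.** The only design figure is 500. It cannot be reproduced or refuted, because no effect size, standard deviation, event rate, alpha, power or dropout is given. No overall error rate is stated to compare with.

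**Counting the outcomes (STUDY ENDPOINTS).**
- LFI: 1.
- Named clinical outcomes: 6 (waitlist placement, waitlist mortality, post-transplant mortality, disposition, number of hospitalisations, duration of hospitalisations).
- Liver-related complications: 1 as a composite, or 6 if analysed by type. The plan does not say which.
- Feasibility: 1.

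The total is 1 + 6 + 1 + 1 = 9, or 1 + 6 + 6 + 1 = 14.

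**Which of these are tested.** The Statistical analysis section names tests for clinical endpoints only. LFI is covered if it counts as a continuous clinical endpoint. No test is named for feasibility. The number of tests k is therefore a range.

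**Formula.** If no outcome truly differs between arms and the k tests are independent, the chance of at least one false positive is 1 − (1 − α)^k. The plan gives no α; two-sided 0.05 per test is assumed here.

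| Outcomes tested | Complications as composite | Complications by type |
|---|---|---|
| Clinical outcomes only | k = 7: 1 − 0.95^7 = 30.2% | k = 12: 1 − 0.95^12 = 46.0% |
| Plus LFI | k = 8: 33.7% | k = 13: 48.7% |
| Plus LFI and feasibility | k = 9: 37.0% | k = 14: 51.2% |

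**Sensitivity to α, for 7 to 14 tests.** At 0.01 the range is 6.8% to 13.1%; at 0.025, 16.2% to 29.8%; at 0.10, 52.2% to 77.1%.

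**Sensitivity to correlation, for 9 to 14 tests at 0.05.** This was simulated with equally correlated normal test statistics, 300,000 draws per setting. The correlations are assumptions.

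| Correlation | 9 tests | 14 tests |
|---|---|---|
| 0.3 | 33% | 44% |
| 0.5 | 27% | 35% |
| 0.8 | 16% | 20% |

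**In the other direction.** Testing LFI at several visits, testing the eight survey items separately, or adding comparisons with the retrospective control group would increase k. The plan does not say how many such tests would be made, so this was not quantified.

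**The case against.** The strongest reply is that this is a pilot, where strict error control matters less. The plan does call itself a pilot. It also sets out to test effectiveness, hypothesises better clinical outcomes, and justifies its sample size by the wish to detect differences between arms. A plan that intends between-arm inference needs a rule for what counts as positive, so this reply softens the point without answering it.

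Three other objections stand, and they limit the size of the claim:

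- A reader might infer that every primary outcome will be tested without adjustment, and so quote only 37% to 51%. The documents do not support that. They name no test for feasibility and cover LFI only by interpretation. They are silent on adjustment; they do not say that none will be made.
- Independence is unlikely. Number and duration of hospitalisations, complications and waitlist mortality plausibly move together, so for a given set of tests the independence figure sits near the upper end.
- For the clinical outcomes, follow-up is bounded by STUDY TIMELINES and a survival analysis is planned. The missing time point is therefore most serious for LFI.

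A reader might also infer that the design could not support mortality or disposition as primary endpoints. That cannot be shown. The documents give no event rates or power, and the 500 covers all groups, including the separate quality-of-life study, so the number to be randomised is unknown. Making every clinical outcome secondary is also partly a matter of preference: the outcomes serve Aim 4, and a Holm or gatekeeping rule would control the error if some stayed primary.

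**Conclusion.** The concern holds. At least nine outcomes are called primary and between-arm tests are planned, but no alpha, hierarchy, multiplicity adjustment, LFI time point or success rule is stated. With an assumed two-sided 0.05 per test, independence and no true difference on any outcome, the chance of at least one false-positive primary result is about 30% to 51%. For 9 to 14 tests with correlation 0.8 it is still 16% to 20%, at least three times the nominal 5%. The exact size depends on an alpha, a correlation and a set of tests that the plan does not fix; the lack of a decision rule does not depend on them. This is more than missing detail, because following the plan as written leaves the choice of primary result open until the data are seen.

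**What to change.** - **One primary efficacy endpoint.** Name one endpoint and one time point for LIFT versus LIFT + REAP. Clinic-measured LFI at the 3-month visit, tested at two-sided 5%, is a suitable example. Say whether the 3 months run from baseline or from randomisation two weeks later, and state a rule for patients who die or are transplanted before the visit.
- **Feasibility.** Report it descriptively with a 95% confidence interval, after defining how the survey is scored.
- **Clinical outcomes.** Make them secondary, with estimates and 95% confidence intervals, either Holm-adjusted or labelled exploratory. Say whether complications form a composite or are analysed by type.
- **If the sponsor keeps any clinical outcome as primary,** test it under a pre-specified Holm or gatekeeping rule. For scale, a plain Bonferroni split of 5% would be 0.05/9 = 0.0056 per test for nine tests, or 0.05/14 = 0.0036 for 14.

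The cost is wording in STUDY ENDPOINTS and the Statistical analysis section, settled before outcome data are examined. The 3-month clinic frailty assessment is already scheduled in both arms, so no new data collection is needed. The downside is that the sponsor can no longer call any single nominally significant clinical outcome a positive primary result.
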